3.2.3 Visit 2: Follow-up with Biofinity/dispensing of first daily disposable lens

Subjects should attend wearing their Biofinity lenses which should have been in situ for at least two hours. Subjects who attend without lenses in situ for at least two hours will usually be rescheduled. The following procedures will be performed (any ocular measurement procedures outlined below will be carried out on each eye):

1. Any medical or ocular issues since the last visit will be recorded.
 2. Lens wearing times since the previous visit will be recorded (hours per day, days per week and comfortable hours per day).
 3. Lens wearing time on study visit day.
 4. Retrieval of any unused lenses (and care solution at Visit 2 only).
 5. [REDACTED]
6. The subject will be asked to score the following with reference to appropriate visual analogue scales (0-100) [REDACTED]:
- Comfort after insertion
 - Comfort before removal
 - Overall comfort
 - [REDACTED]
 - [REDACTED]

- [REDACTED]
- [REDACTED]
- [REDACTED]
- [REDACTED]
- [REDACTED]
- [REDACTED]
- [REDACTED]

7. [REDACTED]

- [REDACTED]
- [REDACTED]
- [REDACTED]
- [REDACTED]
- [REDACTED]
- [REDACTED]
- [REDACTED]
- [REDACTED]
- [REDACTED]
- [REDACTED]
- [REDACTED]
- [REDACTED]
- [REDACTED]
- [REDACTED]
- [REDACTED]

8. [REDACTED]
[REDACTED]
[REDACTED]
[REDACTED]
[REDACTED]
[REDACTED]

9. Lens fit [REDACTED] assessment, as described in section 3.2.2 (including push-up).

10. The investigator will answer the following question: “The fit of the lens is acceptable?” using the following grading scale. If the grade is 3 or more, the reasons why should be stated:

- Strongly agree
- Agree
- Neither agree not disagree
- Disagree
- Strongly disagree

11. The study lenses will be removed and discarded.
12. [REDACTED]
13. The first daily disposable study lens will be fitted and allowed to settle for five minutes, according to the randomisation table [REDACTED]
14. The same procedures as for Visit 1 (section 3.2.2) steps 8-15 will be carried out.
15. [REDACTED]
16. The subject will be discharged and asked to return for a one week follow-up visit wearing the study lenses which need to been worn for at least two hours. Subjects should be asked to wear their lenses for a minimum of eight hours per day, five days per week.

3.2.4 Visit 3: Follow-up first daily disposable lens/dispensing second lens

This visit will be identical to Visit 2 (Section 3.2.3), with the first daily disposable study lens first being assessed, before the second daily disposable lens is fitted, assessed and dispensed. [REDACTED]

[REDACTED]

3.2.5 Visit 4: Follow-up second daily disposable lens

This study visit will be identical to Visit 2 (Section 3.2.3) steps 1-12, with the second daily disposable lens being assessed, [REDACTED] (per 3.2.4) between Biofinity and the second daily disposable lens.

[REDACTED]

[REDACTED] the following will be carried out:

1. At the final visit (or when the subject is discontinued at an earlier visit) the subject will sign a study exit statement acknowledging that the work is complete, although they may have been asked by the investigator to attend a post-study follow-up visit, and that they should continue to use their lenses (and solutions) as advised, and seek aftercare for their contact lenses. A copy of this signed form will be issued to the subject.
2. The subject will be issued with their payment and discharged.

3.2.6 Post-study follow-up visit

In the case of a subject who exits the study with significant clinical signs or symptoms, the investigator must undertake to examine the subject at intervals they determine to be clinically appropriate until the sign or symptom has resolved or returned to a level that is considered to be clinically acceptable. Details from these visits will be recorded on a post-study follow-up visit eCRF.

3.3 Monitoring subject compliance

Subjects are required to adhere to the instructions provided during this clinical investigation. This will be confirmed at the study visits by verbal questioning of the subject by the investigator.

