1.4 Study design

This will be a randomised, double-masked, crossover study, in which 55 subjects who have been 'pre-conditioned' (i.e. fitted) with Biofinity spherical lenses for one month are switched into daily disposable lenses. Subjects will wear each daily disposable lens type for one week, in random order.

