1.5.1 Power analysis

A power analysis for end-of-day comfort has shown that 51 subjects completing the study will provide a sufficient number of subjects for this purpose (non-inferiority testing). This will also provide enough subjects to show non-inferiority between lenses for insertion comfort and overall comfort. To allow for discontinuations, 55 subjects will be dispensed with contact lenses.

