2.1.1 Subject withdrawal and replacement

This study includes four clinical visits. Once the study consent form is signed, the subject is considered to be enrolled on the study. Subjects who have signed the consent form, but who have not completed the dispensing visit will usually be replaced. All subject data will be included in the final analyses unless there are strong grounds for exclusion; such grounds will be detailed in the final report. At the end the study, all subjects will sign a study exit form.

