2.6.1.1 Use of lenses

Biofinity lenses will be worn on a daily wear, reusable basis (i.e. removed at end of day and stored in the provided care system). The two daily disposable study lenses will be worn on a daily wear, daily disposable basis (i.e. removed at end of day and discarded). All lenses should be worn for a minimum of eight hours per day, five days per week. The lenses are also to be worn for a minimum of two hours before attending the follow-up visits.

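### Non-inferiority on comfort is tested on all subject data by default, with undefined exclusions and no prespecified analysis of subjects who met the plan's own wear minimum

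*Combined protocol and SAP*

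**What the plan says.** Section 1.5.1 bases the sample size on non-inferiority: "A power analysis for end-of-day comfort has shown that 51 subjects completing the study" are enough for that purpose. It extends the claim to two further scores: "This will also provide enough subjects to show non-inferiority between lenses for insertion comfort and overall comfort". On recruitment it adds: "To allow for discontinuations, 55 subjects will be dispensed with contact lenses". The design is a crossover (section 1.4): "Subjects will wear each daily disposable lens type for one week, in random order".

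The rule on who is analysed is in section 2.1.1: "All subject data will be included in the final analyses". The same sentence goes on to except cases where there are strong reasons to exclude, to be explained in the final report. No criteria are given. Section 3.4 lets incomplete datasets in where this is judged appropriate.

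The wear requirement is in section 2.6.1.1: "All lenses should be worn for a minimum of eight hours per day, five days per week". Section 3.3 gives the method for checking that subjects follow instructions: "This will be confirmed at the study visits by verbal questioning of the subject by the investigator". The Visit 2 procedures (section 3.2.3) go further:

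- They record hours per day, days per week and wearing time on the visit day.
- They retrieve unused lenses.
- Subjects without two hours of wear are usually rescheduled.

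Sections 3.2.4 and 3.2.5 carry these steps to Visits 3 and 4. Section 2.2 allows the investigator to discontinue subjects who repeatedly refuse to follow instructions or who use other lenses.

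The visible text defines no per-protocol set, no adherence threshold for analysis, no non-inferiority margin and no decision rule.

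**The concern.** In a superiority comparison, poor adherence usually works against the claim. In a non-inferiority comparison it can work for it. Suppose one daily lens is worse, and some subjects wear both lenses so little that they rate them the same. Those subjects pull the mean difference toward zero, and the confidence interval moves inside the margin more often than it should. A conventional guard is a prespecified analysis of adherent subjects beside the all-data analysis. The plan collects what such an analysis needs, and it sets the threshold itself, but does not connect the two.

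The exclusion clause does not fill the gap. Without stated criteria, exclusions can be settled after the data are seen, and they could move the result in either direction. At stake is the one type of claim for which the sample size is justified.

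**Working it through.** **Inputs from the plan.** 51 completers and 55 dispensed (1.5.1), a two-lens crossover (1.4), and a wear minimum of 8 hours a day on 5 days a week (2.6.1.1). I take the comparison to be clariti 1 day against MyDay, following the aim in 1.3.

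**Inputs not in the plan, assumed.** One-sided alpha of 2.5% or 5%, power of 80% or 90%, and 10% or 20% of subjects contributing no lens difference.

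**The plan's own figures.** 51 cannot be reproduced without margin, SD, alpha and power. Going from 51 to 55 leaves room for 4/55 = 7.3% discontinuations; no rate is stated.

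**Step 1: the margin that 51 implies.** For a paired comparison with a true difference of zero, r = margin / SD of the paired difference = (z_alpha + z_power) / sqrt(51). At 2.5% and 80% this is (1.960 + 0.842) / 7.141 = 0.392.

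**Step 2: error with dilution.** Let the true deficit equal the margin and let a share f of subjects contribute zero difference. The error rate is

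Phi( f × r × sqrt(51) / sqrt(1 + f(1 − f)r²) − z_alpha ).

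Example at 2.5%, 80% and f = 0.10: 0.10 × 0.392 × 7.141 = 0.280; divided by sqrt(1 + 0.09 × 0.154) = 1.007 this is 0.278; Phi(0.278 − 1.960) = 4.6%.

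| One-sided alpha | Design power | r | Error, f = 10% | Error, f = 20% |
|---|---|---|---|---|
| 2.5% | 80% | 0.392 | 4.6% | 8.0% |
| 2.5% | 90% | 0.454 | 5.1% | 9.3% |
| 5% | 80% | 0.348 | 8.1% | 12.5% |
| 5% | 90% | 0.410 | 8.8% | 14.3% |

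**Step 3: what if these subjects are also noisier?** Double their SD, so that the variance term 1 becomes (1 − f) + 4f. At f = 10% and alpha 2.5% the error is 4.3-4.7%, a little less than above but still raised. If the lenses are truly equal there is nothing to dilute and the noise only costs power. At f = 10% the variance is 1.3, and power is Phi(0.392 × 7.141 / sqrt(1.3) − 1.960) = 69% where it was 80%. Across both alphas it falls to 69-70% from 80%, and to 81-82% from 90%.

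**Step 4: cost of the adherent set.** If 10% fall outside it, 51 × 0.9 gives 46. With truly equal lenses, power in that set is Phi(0.392 × sqrt(46) − 1.960) = Phi(0.70) = 76%. The 90% design gives 87%. Requiring both analyses to succeed costs slightly more. The two test statistics have correlation sqrt(46/51) = 0.95, and the bivariate normal probability that both pass is about 74% (80% design) or 86% (90% design).

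**The case against.** Several stronger readings are tempting, and the documents do not support them.

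- *Adherence is checked by verbal questioning alone.* Section 3.3 read by itself suggests this. Section 3.2.3 also records wear times, retrieves unused lenses and applies the two-hour rule. The wear times are probably self-reported, and no lens count or reconciliation is specified, but the data exist.
- *Every subject's data must be analysed.* Section 2.1.1 has its exception, section 2.2 allows discontinuation, and section 3.4 addresses spurious data. The fair criticism is that the exclusion rule is undefined, not that it is absent.
- *Under-wear always favours non-inferiority.* It does so only if there is a true lens difference and the under-wearers score the lenses alike. The item scored is comfort before removal, which a subject can rate whenever the lens comes out. Someone who removes an uncomfortable lens early may well score it low, which widens the difference. A subject just short of eight hours is not a zero-difference subject.

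Two objections to the remedy also stand. Wear time is observed after randomisation and may depend on comfort. Restricting to adherent subjects can therefore drop those who cut wear short because a lens was uncomfortable, and so flatter that lens. And returned lenses cannot verify hours: worn lenses are discarded (2.6.3), spare pairs are issued (3.2.2), and each period lasts 7 to 10 days (Table 3).

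Finally, parts of sections 1.5 and 2.9 and of the visit steps are redacted, so a rule under redaction cannot be excluded. Sections 1.5.1, 2.1.1, 3.3 and 3.4 show no redaction.

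None of this supplies the missing link between the wear data and the analysis. The two-hour rule covers visit days only and is applied usually, not always; discontinuation is at the investigator's discretion.

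**Conclusion.** The concern holds in a limited form. The non-inferiority test has an all-data default, an open exclusion clause, and no visible analysis that uses the recorded wear data against the plan's own minimum. This can raise the chance of a false non-inferiority claim when a true deficit exists. In the illustration, 10% zero-difference subjects roughly double a one-sided 2.5% error, and 20% more than triple it; at one-sided 5% the error becomes 8.1-8.8% and 12.5-14.3%.

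These figures rest on assumed alpha and power, a back-solved margin, and non-adherence shares that have no source in the documents. They show that the mechanism matters; they do not estimate the error in this trial. It would also go too far to infer that the all-data analysis is wrong or should be replaced. The point is a cheap improvement, not a fatal flaw.

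**What to change.** Before unmasking, add the following to sections 1.5 and 2.1.1, with a cross-reference in 3.3:

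1. Define a per-protocol set: subjects who completed both daily-lens weeks and met the section 2.6.1.1 minimum by recorded wear times. State how the weekly minimum is read over a period of 7 to 10 days.
2. Record lenses dispensed, including spares, and use dispensed minus returned as a check on days worn only, not on hours.
3. List the grounds for exclusion, to be applied while the data are still masked.
4. Analyse end-of-day comfort in this set beside the all-data set, and claim non-inferiority only if both confidence intervals exclude the margin. The per-protocol result must not replace the all-data result.
5. State the margin, SD of the paired difference, alpha and power behind 51.

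The cost is a few lines of text and a count of lenses already being retrieved; no new visit or measurement is needed. The first downside is the loss of power shown above, of which the allowance of four subjects takes no explicit account. The second is possible selection in the per-protocol set because wear may depend on comfort. The report should therefore list who was left out and why.

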3.4 Missing, unused and spurious data

The absence of any data will be carefully and critically considered. If appropriate, partial datasets will be included in the final analysis. Any data missing from a subject visit will be outlined in the report by indicating the number of subjects included for each analysis. Data that are unused or considered to be spurious will be detailed and discussed in the report.

Section 4. Study co-ordination

4.1 Document processing

All case report forms will be processed and evaluated by Eurolens Research, who will produce the final report with full statistical analysis. A draft report will be sent to the Industrial Contact Person in order to make comments and ask for re-drafts. If no comments are received from the Industrial Contact Person within eight weeks, a final report will be released with a separate document control page (in duplicate), requesting the Industrial Contact Person to sign both copies, one to keep and the other to be returned to Eurolens Research.

4.2 Disclosure

All matters relating to this clinical study are confidential and should only be disclosed to relevant authorised parties. More precise details relating to disclosure are outlined in the Research Agreement. None of the investigators involved in this work owns equity in the funding company.

